#### **8.4.2 Secondary Efficacy Endpoint #1: Frequency and duration of Clinically Significant Cardiac Arrhythmia Events**

Frequency and duration of CSCAs (bradycardia, ventricular tachycardia and/or asystole) events during the 8-week Phase-I dialysate cross-over period and the 8-week Phase-II cross-over period is a secondary efficacy endpoint. Definitions of CSCA events are provided in [Section 5.1.2](#).

This secondary objective will have been achieved if the frequency of post-dialysis CSCAs event (bradycardia, ventricular tachycardia and/or asystole) is lower during experimental compared to standard treatment or if a total duration of post-dialysis CSCAs event (bradycardia, ventricular tachycardia and/or asystole) is shorter during experimental compared to standard treatment.

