### **A Prospective, Randomized, Multi-Center, Open-Label, Cross-Over Study of Sodium Zirconium Cyclosilicate to Control Interdialytic Hyperkalemia Following Augmentation of Dialysate Potassium: Efficacy to Reduce the Incidence of Post-Dialysis Atrial Fibrillation and Clinically Significant Cardiac Arrhythmias - ADAPT Trial**

---

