## Study design

This is a prospective, open-labelled, randomized, 2x2 cross-over design study of 88 patients with end stage renal disease (ESRD) receiving routine out-patient dialysis using a standard 2.0 potassium ion ( $K^+$ )/2.5 calcium ion ( $Ca^{++}$ ) dialysate bath. The overall aim of the study is to determine whether converting stable hemodialysis patients from a “standard” 2.0  $K^+$ /2.5  $Ca^{++}$  dialysate (without Lokelma) to a 3.0  $K^+$ /2.5  $Ca^{++}$  mEq dialysate supplemented with the orally administered potassium binder sodium zirconium cyclosilicate (Lokelma®) to treat interdialytic hyperkalemia will reduce the incidence and duration of post-dialysis atrial fibrillation.

Following screening, eligible subjects will undergo placement of an implantable cardiac loop recorder (LINQ device) to monitor for the development of atrial fibrillation or any clinically significant cardiac arrhythmias [CSCA]). After a two-week recovery period (to allow the patient to heal from cardiac loop recorder placement), patients will be randomized (1:1 ratio) to one of two treatment sequences:

- Sequence **A**: standard 2.0  $K^+$ /2.5  $Ca^{++}$  dialysate with no Lokelma supplementation for two (2) months, followed by a cross-over to experimental 3.0  $K^+$ /2.5  $Ca^{++}$  dialysate with Lokelma supplementation (on off-dialysis days) for two (2) months;

Or

- Sequence **B**: experimental 3.0  $K^+$ /2.5  $Ca^{++}$  dialysate with Lokelma supplementation (on off-dialysis days) for two (2) months, followed by standard 2.0  $K^+$ /2.5  $Ca^{++}$  dialysate with no Lokelma supplementation for two (2) months.

Each two-month treatment period (both 2.0  $K^+$ /2.5  $Ca^{++}$  dialysate and 3.0  $K^+$ /2.5  $Ca^{++}$  dialysate with Lokelma sequences) will be preceded by a two-week run-in period, to allow the patient to adapt to the new dialysate bath.

While receiving the higher  $K^+$  dialysate, patient will be treated on off-dialysis days (4 days/week) with Lokelma, titrated to maintain  $K^+$  between 4.0 and 5.5 mEq/L. Refer to section 7.2 for the initial dose and frequency details.

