**Figure 1 - Effect of Dialysate Potassium on the Incidence of Sudden Cardiac Arrhythmia**

Source: *Pun et al. 2011*

[figure not shown]
This important paper suggests that a  $K^+$  of 5.0 mEq/L may be optimal for preventing dialysis-associated arrhythmias. The observation that differences in dialysate  $K^+$  levels markedly affected arrhythmia rates suggested that dialysis itself could be contributing to the markedly elevated sudden death rates among ESRD patients. To examine this question, Roy-Chaudhury and Tumlin et al. conducted the Monitoring in Dialysis (MID) Study in which 66 patients receiving outpatient hemodialysis underwent placement of the Reveal XT or Reveal LINQ (Medtronic, Minneapolis, MN) insertable cardiac monitoring device. This device allows for continuous and long-term detection of both atrial and ventricular arrhythmias before and after a dialysis for periods of up to 30 days. In this purely observational trial, participating patients were maintained on their standard dialysis prescription and the incident rates of atrial fibrillation, bradycardia, ventricular tachycardia, and asystole were monitored for 6 months. The study used a vigorous definition for atrial fibrillation requiring a minimum of a 6-minute duration to be considered clinically significant. As shown in **Figure 2**, 42% of patients experienced a clinically significant atrial fibrillation event during the 6 months of study. In addition, the rates of atrial fibrillation paralleled the “dialysis week”, showing the highest rates during dialysis, but also showing significantly increased event rates for up to 12 hours after completion of a dialysis session. Moreover, when the investigators examined the difference in arrhythmia rates between patients being dialyzed with a 2.0  $K^+$  dialysate versus a 3.0  $K^+$  bath, there was a statistically lower rate of arrhythmias among patients dialyzed with the 3.0  $K^+$  bath ( $P < 0.0015$ ) (*Roy-Chaudhury et al. 2018*).

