**Figure 6 - Study Flow Chart**

## 2. STUDY OBJECTIVES

### 2.1 Primary Objective

Primary Objective: Atrial Fibrillation Rates	Primary Outcome Measure:

To demonstrate whether increasing the K+ concentration in a standard hemodialysis bath from 2.0 K+/2.5 Ca++ to a 3.0 K+/2.5 Ca++ composition with SZC will reduce the incidence of atrial fibrillation events. [1]
	
➤ Frequency of atrial fibrillation events [1] occurring during the 8-week Treatment Phase-1 and the 8-week Treatment Phase-2 dialysate cross-over periods.

Abbreviations: CSCA=clinically significant cardiac arrhythmia

[1] Atrial fibrillation will be defined as irregular heart rhythms and irregular R-R intervals in the absence of definable P waves for a minimum of 6 minutes. Each atrial fibrillation event will be adjudicated and validated as a true atrial fibrillation event by a central cardiologist who is blinded to dialysate K+ content.

[2] Experimental treatment (8 weeks): hemodialysis using 3.0K+/2.5 Ca++ dialysate bath, with sodium zirconium cyclosilicate (Lokelma®) supplementation on off-treatment days

[3] Standard treatment (8 weeks): hemodialysis using 2.0K+/2.5 Ca++ dialysate bath, without sodium zirconium cyclosilicate (Lokelma®) supplementation

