### 2.2 Secondary Objectives

Secondary Efficacy Objective #1: Clinically Significant Cardiac Arrhythmia Rates	Secondary Outcome Measure:

To determine whether the incidence and duration of post-dialysis CSCAs (defined as bradycardia, ventricular tachycardia and/or asystole [1]) observed during experimental treatment [2] will be reduced compared to standard treatment. [3]
	
➤ Frequency of CSCAs (bradycardia, ventricular tachycardia and/or asystole) [1] occurring during the 8-week Treatment Phase-1 and the 8-week Treatment Phase-2 dialysate cross-over periods.
 
➤ Total duration of CSCAs (bradycardia, ventricular tachycardia and/or asystole) [1] occurring during the 8-week Treatment Phase-1 and the 8-week Treatment Phase-2 dialysate cross-over periods.

Secondary Efficacy Objective #2: Events Outside the Optimal K + “Window”	Secondary Outcome Measure:

To determine whether the addition of oral sodium zirconium cyclosilicate (Lokelma®) during the 2-month treatment phase with the 3.0 K+/2.5 Ca++ dialysate bath will reduce risk of weeks outside the “K+ safety range” of 4.0 to 5.5 mEq/L compared to the 2-month treatment phase with the 2.0 K+/2.5 Ca++ dialysate bath.
	
➤ Whether or not K+ outside of the 4.0 to 5.5 mEq/L safety range (Yes/No binary outcome measure).
 
The risk of weekly events of pre-dialysis K+ or the risk of post-dialysis K+ falling outside the “K+ safety range” will be compared between the two dialysate groups.

Abbreviations: CSCA=clinically significant cardiac arrhythmia

[1] CSCA events are defined as follows:

- Bradycardia: Heart rate of  $\leq 40$  beats per minute (BPM) for a minimum duration of 6 seconds.
- Ventricular Tachycardia: Regular tachy-arrhythmia of  $\geq 130$  BPM for a minimum duration of 30 seconds
- Asystole: Absence of detectable ventricular conduction for a minimum of 3 seconds

[2] Experimental treatment (8 weeks): hemodialysis using 3.0K+/2.5 Ca++ dialysate bath, with sodium zirconium cyclosilicate (Lokelma®) supplementation on off-treatment days

[3] Standard treatment (8 weeks): hemodialysis using 2.0K+/2.5 Ca++ dialysate bath, without sodium zirconium cyclosilicate (Lokelma®) supplementation

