### **8.4 Outcome Measures for Analyses**

#### **8.4.1 Primary Efficacy Endpoint: Frequency of Atrial Fibrillation Events**

The primary efficacy endpoint is the frequency of atrial fibrillation events occurring during the 8-week Treatment Phase-1 and the 8-week Treatment Phase-2 dialysate cross-over periods. Atrial fibrillation will be defined as irregular heart rhythms and irregular R-R intervals in the absence of definable P waves for a minimum of 6 minutes. Each atrial fibrillation event will be adjudicated and validated as a true atrial fibrillation event by a central cardiologist who is blinded to dialysate K+ content.

The total number of atrial fibrillation events will be compared between the two dialysate groups.

The primary objective of the study will have been achieved if the frequency of atrial fibrillation events occurring during experimental treatment (hemodialysis using 3.0K+/2.5 Ca++ dialysate bath, with Lokelma supplementation on off-treatment days) is lower compared to standard treatment (hemodialysis using 2.0K+/2.5 Ca++ dialysate bath, without Lokelma supplementation).

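### Section 8.4.2 defines the CSCA endpoint over all hours of each 8-week phase but judges success on post-dialysis CSCAs, a term the protocol never defines

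*Protocol*

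**What the plan says.** **CSCA objective.** Section 2.2 and the synopsis set the aim: "To determine whether the incidence and duration of post-dialysis CSCAs (defined as bradycardia, ventricular tachycardia and/or asystole [1"]) will be lower on experimental treatment. Section 5.1.2 repeats the post-dialysis qualifier.

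**CSCA endpoint.** The outcome measures beside that objective, and the first sentence of section 8.4.2, are the frequency and total duration of CSCAs during the two 8-week phases. Neither carries a time restriction.

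**CSCA success rule.** The next paragraph of 8.4.2 reads "This secondary objective will have been achieved if the frequency of post-dialysis CSCAs event" is lower on experimental treatment, or if the total duration of post-dialysis CSCAs is shorter.

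**Analysis.** Section 8.5.3 analyses CSCA frequency like the primary endpoint. Section 8.5.2 models that endpoint with the log of the period's duration as offset. Total CSCA duration goes into a linear mixed model. No post-dialysis count is specified.

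**AF.** The title promises "Efficacy to Reduce the Incidence of Post-Dialysis Atrial Fibrillation and Clinically Significant Cardiac Arrhythmias", and the overall aim (synopsis and section 1.4) is that the experimental regimen "will reduce the incidence and duration of post-dialysis atrial fibrillation". The formal primary objective in section 2.1 is only that it "will reduce the incidence of atrial fibrillation events". Section 8.4.1 follows suit: "The primary efficacy endpoint is the frequency of atrial fibrillation events occurring during the 8-week Treatment Phase-1" and the matching second phase, and "The total number of atrial fibrillation events will be compared between the two dialysate groups".

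**Time frame.** The only one is in the background. Section 1.1.1 describes an observational loop-recorder study with AF rates highest during dialysis and "showing significantly increased event rates for up to 12 hours after completion of a dialysis session"; section 1.1 gives the same 12 hours.

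**The concern.** A success rule should be decidable from the endpoint and analysis specified for it. Here the rule concerns one quantity and the analysis estimates another. Either the rule in 8.4.2 cannot be evaluated, or an all-hours result will be reported under a post-dialysis label. The two can differ in either direction: post-dialysis CSCAs could fall with little change in the total, or the total could fall with post-dialysis CSCAs unchanged.

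The undefined term adds to this. It is unclear whether events during a session count, and how long after a session the period lasts. The protocol's own usage does not settle it: section 4.2.1 calls electrolytes post-dialysis when the sample is drawn before the session ends.

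What is at stake is what the trial may conclude about CSCAs, and how the title and aim describe the AF result.

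**Working it through.** **1. The plan's own figure.** The sample size in section 8.2 concerns AF over all hours. Inputs: control rate 4.6 (time unit not stated; taken as per 8-week period), rate ratio 0.75 so 3.45 on experimental treatment, overdispersion 0.07, and 80 completers (40 per sequence). With ρ the between-period correlation of the patient effect:

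var(log RR) = [1/4.6 + 1/3.45 + 2 × 0.07 × (1 − ρ)] / 80

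Power is 89.2% at ρ = 0 and 95.1% at ρ = 1 (simulated: 90.0% and 95.6%). The plan's figure of more than 90% is reproduced, and nothing in this point alters it.

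**2. The texts side by side.**

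| Element | CSCA | AF |
|---|---|---|
| Title, overall aim | Post-dialysis in the title; CSCA not in the aim | Post-dialysis |
| Formal objective | Post-dialysis (2.2) | No restriction (2.1) |
| Endpoint | All events in each phase (2.2, 8.4.2) | All events in each phase (2.1, 8.4.1) |
| Analysis | Whole period (8.5.2, 8.5.3) | Whole period (8.5.2) |
| Success rule | Post-dialysis (8.4.2) | No restriction (8.4.1) |

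For AF, the formal elements agree and only the title and aim stand apart. For CSCA, the objective and success rule conflict with the endpoint and analysis.

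**3. How far the quantities can differ (illustration only).** Hours: a phase has 8 × 168 = 1,344 hours. Three sessions a week (inclusion criterion 3) give 24 sessions per phase. A 12-hour window after each gives 288 hours, a fraction f = 288/1,344 = 36/168 = 0.214. Adding an assumed 4-hour session gives f = 48/168 = 0.286.

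If the event rate inside the window is r times that outside, the share of events inside is s = f·r / (f·r + 1 − f). A reduction d confined to the window lowers the total by s·d. A reduction d confined to other hours lowers it by (1 − s)·d. Take d = 25%, borrowed from the AF planning because no CSCA effect is planned:

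| f | r | s | Fall in total, effect only inside | Fall in total, effect only outside |
|---|---|---|---|---|
| 0.214 | 1 | 0.214 | 5% | 20% |
| 0.214 | 2 | 0.353 | 9% | 16% |
| 0.214 | 3 | 0.450 | 11% | 14% |
| 0.286 | 1 | 0.286 | 7% | 18% |
| 0.286 | 2 | 0.444 | 11% | 14% |
| 0.286 | 3 | 0.545 | 14% | 11% |

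The values of r, the 4-hour session, the use of 12 hours for CSCAs and the confinement of the effect are all assumptions. The right-hand column is the case where the total falls although post-dialysis events have not changed.

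**The case against.** The fair case for the plan is that the formal endpoints are clear, the recorder runs continuously through both phases, and the protocol defers technical detail to a statistical analysis plan that is not shown and could define a window. The affected rule is secondary, with nominal p-values and no multiplicity control. Post-dialysis may be only a loose adjective for arrhythmias in dialysis patients.

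Most of this stands as a limit on the point. It does not remove it, because the success rule, the endpoint and the whole-period analysis are all fixed in the protocol and disagree there.

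A reader might infer more, which the documents do not support:

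- *That the trial cannot show a post-dialysis effect.* Continuous recording means a window can still be applied to recorded events.
- *That the primary analysis misses its question.* The primary objective, hypothesis and success rule carry no post-dialysis limit and match the all-hours count.
- *That a fall arising from Lokelma on off-dialysis days would be spurious.* The tested treatment is the 3.0 K+ bath together with Lokelma, so that would be an effect of the package.
- *That the trial is underpowered through dilution.* The planned 25% is a reduction in the overall AF rate. Nothing says the effect is confined to a window.
- *That most counted events fall outside the window.* Hours are not events. With f = 0.214, more than half the events fall inside once r exceeds 0.786/0.214, about 3.7, and the documents give no value of r.
- *That session times are not collected.* Table 1 and section 4.1.6 do not list them, but the eCRF is not shown, and section 4.1.4 shows that dialysis flow sheets exist.

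**Conclusion.** The point holds for the CSCA endpoint. Section 8.4.2 contradicts itself, secondary objective #1 and section 5.1.2 share the undefined qualifier, and the specified whole-period analysis cannot by itself support a post-dialysis conclusion. For AF, only the title and overall aim go beyond what is counted; the all-hours primary endpoint and its sample size are sound on this point and should not change.

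This rests on the wording alone and needs no numerical assumption. Its numerical size is unknown, because the share of events that fall post-dialysis is not in the documents. The percentages above show only that the two quantities can differ materially. The correction is worth making because it is cheap and decides what the trial may say about CSCAs.

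**What to change.** Leave the all-hours AF primary endpoint as it is, and choose one of two routes for the rest.

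**Route 1: remove the qualifier.** Delete post-dialysis from secondary objective #1 (synopsis and 2.2), section 5.1.2, the 8.4.2 success rule, the title, the overall aim (synopsis and 1.4), and any conclusion drawn from all-hours counts. The cost is editing only.

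**Route 2: define it.** Pre-specify a post-dialysis window, state whether events during the session belong to it, and base the 8.4.2 statement on CSCAs with onset in that window. Use hours at risk in the window as the offset for frequency, and restrict total duration to the same events. If 12 hours is used, state that this figure is a background result for AF and that applying it to CSCAs is an assumption. Any post-dialysis wording kept for AF would need a corresponding windowed secondary count; otherwise delete it there too.

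Route 2 needs session start and stop times for Weeks 3–10 and 13–20, for example from dialysis run sheets. If they are not already captured, that is 48 sessions × 2 fields = 96 entries per patient, or 8,448 for 88 patients, plus one further analysis. The windowed count will also contain fewer events and so be less precise.

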#### **8.4.3 Secondary Efficacy Endpoint #2: Events Outside the Optimal K+ “Window”**

The number of events of K+ outside of the 4.0 to 5.5 mEq/L safety range is a secondary efficacy endpoint in this study, The total number of events of pre- or post-dialysis K+ falling outside the “K+ safety range” will be averaged and compared between the two dialysate groups.

The study aims to show that patients experience less risk of K+ falling outside the range of 4.0 to 5.5 mEq/L while receiving experimental compared to standard treatment.

#### **8.4.4 Exploratory Efficacy Endpoint #1: Relationship Between PBUTs and Atrial Fibrillation Rates**

The study will also evaluate the correlation between PBUTs (indoxyl sulfate, PCS, and ADMA) and the frequency of atrial fibrillation events.

#### **8.4.5 Exploratory Efficacy Endpoint #2: Correlation Between Electrolytes and Clinical Events**

The following correlations will be explored:

- Correlation between electrolyte levels and clinical events (intradialytic hypotension, muscle cramping, and cardiac arrhythmias).
- Correlation between electrolytes falling below threshold levels (Ca++ < 7.0 mEq/L, PO4 levels <3.0 mEq/L, Mg++< 2.0 mg/dl, and K+ of < 3.5 mEq/L) and clinical events (cardiac arrhythmias).

#### **8.4.6 Safety Endpoint #1: Lokelma Induced Hypokalemia**

To evaluate whether the use of Lokelma during periods when patients are receiving a 3.0 K+/2.5 Ca++ bath is associated with hypokalemic events, the total number of hypokalemic events (defined as Piccolo POCT or laboratory-measured K+ of < 3.5 mEq/L) will be summarized.

